2.4. Sample Size Justification

30 subjects as investigational product vaccinated subjects

Rationale

The sample size was set at 30 subjects who are eligible for inclusion in a stratified analysis for exploring the causes of any differences that may be found in efficacy or safety between intramuscular

administration (this study) and subcutaneous administration (study BK1310-J01), based on the sample size that was used in the intramuscular administration study that was conducted for the vaccine that has already been approved (VaxemHIB aqueous suspension for injection).

Additionally, a simulation found that the probability of a solicited adverse event that has an incidence of 5.8% occurring in a single subject if the sample size is 30 would be 83%. The figure of 5.8% was chosen because this was the incidence of the least frequently reported solicited adverse drug reaction in the BK1310 group in the Japanese phase 2 study of MT-2301 (study MT-2301-J01).

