7.1.3. Confidence Intervals (e.g., Seroprotection rate, Incidence)

When calculating the confidence intervals for the incidences of adverse events, etc., or the antibody seroprotection rates, Clopper & Pearson method will be used.

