7.1.5. Display of Treatment Groups

The display of the treatment groups will be handled as shown in the following table.

Table 7.1.5: Treatment Groups

Treatment Groups	Display
BK1310 0.5 mL per dose	BK1310

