7.5.3. Issues in Statistical Analyses

7.5.3.1. Adjustments for Covariates

Not planned

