7.5.3.8. Analyses of Subgroups

Not planned

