7.6.1.1. Adverse Event Incidences

Analysis population(s): Safety analysis set

Analysis parameter: Adverse events (solicited adverse events, immediate reactions, other), adverse drug reactions (solicited adverse events, immediate reactions, other), serious adverse events, serious adverse drug reactions, adverse events leading to discontinuation, adverse drug reactions leading to discontinuation

Analysis method: The number and proportion (and 95% confidence interval thereof) of subjects experiencing each type of event will be calculated.

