11. OUTPUT LISTINGS

Table Number	Contents
Table 14.1.1.1	Analysis Populations – All Enrolled Subjects
Table 14.1.1.2	Subject Disposition – All Enrolled Subjects
Table 14.1.2.1	Demographics – FAS
Table 14.1.2.2	Demographics – SAF
Table 14.2.1	Seroprotection Rate- FAS
Table 14.2.2.1	Seroprotection Rate (≥ 0.15) for Anti PRP Antibodies-FAS

Table 14.2.2.2	Antibody Titer by Visit -FAS
Table 14.3.1.1	Overall Summary of Adverse Events – SAF
Table 14.3.1.2	Adverse Events by System Organ Class and Preferred Term – SAF
Table 14.3.1.3	Adverse Drug Reactions by System Organ Class and Preferred Term – SAF
Table 14.3.1.4	Serious Adverse Events by System Organ Class and Preferred Term – SAF
Table 14.3.1.5	Serious Adverse Drug Reactions by System Organ Class and Preferred Term – SAF
Table 14.3.1.6	Adverse Events Leading to Discontinuation of Study Drug by System Organ Class and Preferred Term – SAF
Table 14.3.1.7	Adverse Drug Reactions Leading to Discontinuation of Study Drug by System Organ Class and Preferred Term – SAF
Table 14.3.1.8	Adverse Events by Maximum Severity by System Organ Class and Preferred Term – SAF
Table 14.3.1.9	Adverse Drug Reactions by Maximum Severity by System Organ Class and Preferred Term – SAF
Table 14.3.1.10	Pre-specified Adverse Events by Number of study drug injections by System Organ Class and Preferred Term – SAF
Table 14.3.1.11	Pre-specified Adverse Drug Reactions by Number of study drug injections by System Organ Class and Preferred Term – SAF
Listing 16.2.1.1	Subject Disposition – Subjects of Withdrawer
Listing 16.2.1.2	Analysis Populations - All Enrolled Subjects
Listing 16.2.2.1	Demography - All Enrolled Subjects
Listing 16.2.2.2	Concomitant Medications - All Enrolled Subjects
Listing 16.2.3	Administration of study drug- SAF
Listing 16.2.4	Antibody Titer - All Enrolled Subjects
Listing 16.2.5.1	Adverse Events – SAF
Listing 16.2.5.2	Adverse Drug Reactions – SAF

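### Does the sample size of 30 lose its basis because no stratified intramuscular-versus-subcutaneous analysis is planned?

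*SAP*

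**What the plan says.** Protocol 6.1 and SAP 2.4 give the same two-paragraph rationale for 30 vaccinated subjects.

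- **First paragraph.** "The sample size was set at 30 subjects who are eligible for inclusion in a stratified analysis for exploring the causes of any differences" between this study and J01. The rest of the sentence makes those differences conditional on being found, and bases the number on the size of an intramuscular study of an already approved Hib vaccine.
- **Second paragraph.** "a simulation found that the probability of a solicited adverse event that has an incidence of 5.8% occurring in a single subject" is given as 83% with 30 subjects.

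The analysis sections cover J02 alone.

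- Protocol 13.3 plans rates, geometric means and confidence intervals, and 13.3.4 rules out tests.
- SAP 7.1.5 ("The display of the treatment groups will be handled as shown in the following table") has a single row, BK1310.
- SAP 7.1.3 names one interval method for rates: "Clopper & Pearson method will be used". This is a method for a single proportion.
- Under "Adjustments for Covariates" (7.5.3.1) and "Analyses of Subgroups" (7.5.3.8) the SAP enters that nothing is planned.
- SAP 11 lists the efficacy tables, beginning with "Seroprotection Rate- FAS". None has a J01 column or a stratum.
- SAP 7.6.1.1 covers safety: "The number and proportion (and 95% confidence interval thereof) of subjects experiencing each type of event will be calculated".

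**The concern.** A reader who traces the sample-size rationale forward finds nothing at the other end. SAP 2.4 says the subjects are to be usable in a stratified analysis, while SAP 7.5.3.8 plans no subgroups. J01 appears in the background, design, dose and sample-size text but in no analysis section of either document.

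The route comparison also matters to the programme. Protocol 1(4) gives the aim of adding intramuscular use to the approved administration, and Protocol 5.2.1 defends the uncontrolled design on the ground that the two routes do not seem to differ much. J01 is therefore the natural reference. It has two cohorts, and Cohort 1 tests two Hib antigen amounts, so several comparator groups are possible. If comparator, time points, strata and interval method were all chosen after the results were known, the choice could favour a reassuring picture. That would put at risk the credibility of any statement that the routes agree.

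**Working it through.** **1. The plan's own figure.** Inputs from SAP 2.4: incidence 0.058, n = 30.

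- At least one affected subject: 1 − (1 − 0.058)^30 = 1 − 0.942^30 = 1 − 0.1665 = 0.8335, or 83.3%. The plan says 83%.
- Exactly one affected subject: 30 × 0.058 × 0.942^29 = 0.308.

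The intended meaning is at least one, and the figure is right. The incidence tables in SAP 7.6.1 report what this reason needs.

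**2. Where 30 comes from.** The first paragraph gives no power, effect size, margin, strata or J01 group size, so 30 cannot be derived from a J02/J01 comparison. It is taken from the earlier intramuscular study. Without the stratified clause, the precedent and the 83% remain and N is still 30.

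**3. What the planned analyses deliver.** Clopper-Pearson 95% intervals, as in SAP 7.1.3:

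| Seroprotected | 95% interval |
|---|---|
| 30/30 | 88.4% to 100% |
| 28/30 | 77.9% to 99.2% |
| 27/30 | 73.5% to 97.9% |

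None of these uses J01 data or a stratum. They are valid whether or not a cross-study analysis is ever done.

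**4. What the missing analysis could show.** The size of the J01 comparator group is not in the documents. Assume 100 or 200 subcutaneous subjects with 70% local reactions, and 50% (15/30) in J02. Newcombe's interval for d = p1 − p2, with Wilson limits (l, u) for each rate, is

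lower = d − √[(p1 − l1)² + (u2 − p2)²], upper = d + √[(u1 − p1)² + (p2 − l2)²].

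- 15/30 has Wilson limits 0.332 to 0.668, and 70/100 has 0.604 to 0.781. The interval is −0.20 − √(0.168² + 0.081²) to −0.20 + √(0.168² + 0.096²), or −38.7 to −0.6 points.
- With 140/200 as comparator it is −37.9 to −1.9 points.
- In one J02 stratum of 15 (assumed even split), 7/15 against 70/100 gives −46.6 to +1.8 points.

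A 20-point difference barely excludes zero with all 30 subjects, and a stratum of 15 cannot separate a 23-point difference from none. The comparison would be descriptive wherever it was written down.

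**5. Protocol and SAP side by side.** Protocol 13.3 contains no J01 comparison, so the SAP has not dropped a planned analysis, and its statement in section 9 of no changes from the protocol is consistent with that. SAP 1 limits the document to this study. An analysis that depends on J01 data, and on a difference first being seen, need not sit in it.

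**The case for a change.** The strongest case for a change is that exploratory work can still name its comparator and strata in advance, and that a stated basis for the sample size should lead to an analysis or to a citation. The remedy would be cheap: a short SAP section using variables already collected (age group, simultaneous vaccination, baseline titre), a reference to an integrated plan, or deletion of one clause in two places. If nothing is fixed before lock, Protocol 13.4 makes any such comparison an addition to the plan, so the first reason for N would be met only by a post hoc analysis.

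Part of this stands. The link is missing, and the documents neither cite nor exclude a cross-study plan. The harm does not follow. Protocol 13.4 is itself the safeguard: a late comparison must be justified and its results distinguished from the planned ones. With no tests and no success criterion, late choice of strata cannot inflate a formal error rate. Prespecification would also protect less than it usually does, because J02 is open-label and J01 Cohort 1 results after the third dose had already informed the choice of Hib antigen amount (Protocol 5.2.1). The fuller remedy would commit the sponsor to a contrast across studies for nine antibody parameters, which goes well beyond a conditional look at causes. Statisticians could reasonably disagree on whether it would inform or mislead.

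**Conclusion.** The observation is accurate, but no change to the plan follows. It is a minor gap in traceability. The number 30 rests on precedent and on a probability that reproduces (83.3% against 83%), and the planned single-arm estimates and intervals are sound as written. Citing a cross-study plan or deleting the clause would tidy the text, but would alter no result, no conclusion and not N. Adding the comparison would bring little: under the assumptions above, intervals about 36 to 38 points wide with all 30 subjects and about 48 points wide in a stratum of 15.

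This conclusion rests on reading the first paragraph as a contingent follow-up, which its conditional wording supports, and on any J02/J01 comparison being reported as exploratory and non-randomised. The widths depend on assumed J01 group sizes and reaction rates. The conclusion does not, because no planned J02 analysis uses them.

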3. ENDPOINTS

3.1. Efficacy Endpoints

(1) Primary endpoint

The anti-PRP antibody seroprotection (antibody titer $\geq 1 \mu\text{g/mL}$) rate, and the seroprotection rates for pertussis, diphtheria toxin, tetanus toxin, and attenuated polio virus at 4 weeks after the primary immunization

(2) Secondary Endpoints

- 1) The anti-PRP antibody seroprotection (antibody titer $\geq 0.15 \mu\text{g/mL}$) rate and the geometric mean antibody titer for anti-PRP antibodies at 4 weeks after the primary immunization
- 2) The anti-PRP antibody seroprotection (antibody titer $\geq 1 \mu\text{g/mL}$) rate, at a concentration of $1 \mu\text{g/mL}$ or above, and the anti-PRP antibody seroprotection (antibody titer $\geq 0.15 \mu\text{g/mL}$) rate and the geometric mean anti-PRP antibody titer for anti-PRP antibodies at 4 weeks after the booster immunization
- 3) The geometric mean antibody titers for pertussis, diphtheria toxin, tetanus toxin, and attenuated poliovirus at 4 weeks after the primary immunization
- 4) The antibody seroprotection rates and geometric mean antibody titers for pertussis, diphtheria toxin, tetanus toxin, and attenuated poliovirus at 4 weeks after the booster immunization

3.2. Safety Endpoints

Adverse events and adverse drug reactions

3.3. Other Endpoints

None

4. DEFINITIONS OF DERIVED VARIABLES AND TABULATION METHODS

4.1. Methods of Derivation

(1) Age in months

The age in months will be calculated based on the date of the first vaccine dose and the date of birth. The difference between the date in question (YYYY1/MM1/DD1) and the date of birth

(YYYY2/MM2/DD2) will be defined as A.

$$A = (YYYY1 - YYYY2) \times 12 + (MM1 - MM2)$$

If DD1 < DD2, then the age in full months will be A - 1.

If DD1 ≥ DD2, then the age in full months will be A.

(2) Age in months at adverse event onset

The age in months at adverse event onset will be calculated from the date of onset of the adverse event and the date of birth. Additionally, the date in question in “4.1. (1) Age in Months” in this document will be reclassified as the date of adverse event onset in the calculation formula.

(3) Number of days from the immediately preceding dose of investigational product to adverse event onset

The “number of days from the immediately preceding dose of investigational product to adverse event onset” will be calculated as the day of adverse event onset minus the day of the immediately preceding dose. Furthermore, the day of adverse event onset will be the “day on which symptoms were observed or the day of the test that yielded abnormal findings.”

(4) Adverse event duration

$$\text{Adverse event duration} = \text{Date of outcome} - \text{Date of onset} + 1 \text{ (in days)}$$

4.2. Methods of Tabulation

(1) Antibody titer geometric mean and geometric standard deviation

$$\text{Antibody titer geometric mean} = 10^{(\text{mean of the log-transformed value (base 10) of the antibody titer})}$$

$$\text{Antibody titer geometric standard deviation} = 10^{(\text{standard deviation of the log-transformed value (base 10) of the antibody titer})}$$

$$\text{Antibody titer geometric mean 95\% confidence interval}$$

$$= 10^{(\text{lower limit of the 95\% confidence interval of the mean of the log-transformed value (base 10) of the antibody titer})} \text{ to } 10^{(\text{upper limit of the 95\% confidence interval of the mean of the log-transformed value (base 10) of the antibody titer})}$$

However, for the anti-poliovirus antibody titers (anti-poliovirus serotype 1, 2, and 3 antibody titers), because the data obtained are base 2 log-transformed values, they will be calculated as shown below. In this case, the data obtained will be calculated as “the log-transformed values (base 2) of the antibody titers.”

$$\text{Antibody titer geometric mean} = 2^{(\text{mean of the log-transformed value (base 2) of the antibody titer})}$$

$$\text{Antibody titer geometric standard deviation} = 2^{(\text{standard deviation of the log-transformed value (base 2) of the antibody titer})}$$

$$\text{Antibody titer geometric mean 95\% confidence interval}$$

$$= 2^{(\text{lower limit of the 95\% confidence interval of the mean of the log-transformed value (base 2) of the antibody titer})} \text{ to } 2^{(\text{upper limit of the 95\% confidence interval of the mean of the log-transformed value (base 2) of the antibody titer})}$$

(2) Antibody seroprotection rates

Table 4.2

Measurement Parameter		Measurement Method	Reference Value
Hib	Anti-PRP antibody concentrations	Enzyme-linked immunosorbent assay (ELISA)	$\geq 1 \mu\text{g/mL}$ $\geq 0.15 \mu\text{g/mL}$
Diphtheria	Anti-diphtheria antibody concentrations	Neutralization method	$\geq 0.1 \text{ IU/mL}$
Pertussis	Anti-pertussis antibody concentrations	Enzyme-linked immunosorbent assay (ELISA)	$\geq 10.0 \text{ EU/mL}$
	Anti-FHA antibody concentrations		$\geq 10.0 \text{ EU/mL}$
Tetanus	Anti-tetanus antibody concentrations	Indirect agglutination (KPA)	$\geq 0.01 \text{ IU/mL}$
Polio	Anti-poliovirus antibody titers* (types 1, 2, and 3)	Neutralization method	$\geq 8\text{-fold}$

The seroprotection rates for the aforementioned reference antibodies following immunization with the investigational product will be calculated.

Antibody seroprotection rate (%) =

$[(\text{Number of subjects with antibodies}) / (\text{Number of subjects evaluated for efficacy})] \times 100$

The number of subjects assessed for efficacy will be the number of subjects for whom antibody titer results have been obtained.

(3) Adverse drug reactions

Adverse events for which it is thought there is a reasonable possibility of there being a causal relationship with the investigational product are considered adverse drug reactions.

5. ANALYSIS SETS

The analysis of efficacy is performed in the full analysis set (FAS). In addition, safety analysis is performed in the safety analysis set.

The analysis sets are defined below. Detailed rules about subject handling will be decided by the study sponsor before the database lock.

5.1. Efficacy Analysis Sets

The FAS will consist of all enrolled subjects except for the following subjects.

- Subjects who did not take the investigational product at all
- Subjects for whom no antibody titer results at all could be obtained at 4 weeks after the primary immunization

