2.3. Assessment Time Point

	Day of consent	Visit 1		Visit 2		Visit 3		Visit 4		Visit 5		Visit 6	At discontinuation
		1st Vaccination		2nd Vaccination		3rd Vaccination		Post-vaccination Examination 1		4th Vaccination		Post-vaccination Examination 2	
		Before	After	Before	After	Before	After	Vaccination	Before	After	Vaccination	After	
Allowable window		D1		Visit 1 + 3 - 8 weeks		Visit 2 + 3 - 8 weeks		Visit 3 + 4 - 6 weeks		Visit 3 + 6 - 13 months		Visit 5 + 4 - 6 weeks	
Written informed consent		•											
Investigation of subject background			•								•		
Examination		•		• ¹	•		• ¹	•	• ¹	•	•	• ¹	•
Body temperature measurement (axillary)		•			•			•			•		
Investigational product vaccination				•		•		•			•		
Blood sampling (antibody titer)		•								•	•		• ²
Adverse events ³				←					→				
e-Diary ⁴				•		•		•		•			•

*1: Subjects will be asked to wait in the hospital for 30 minutes after receiving the investigational product, and will be examined 30 minutes after immunization.

*2: Blood samples will be collected for antibody titer measurement only at discontinuation after the third or fourth dose of the investigational product has been administered.

*3: An investigation will be performed to confirm whether or not the subject experienced any adverse events during the period from Visit 1 to Visit 4, and during the period from Visit 5 to Visit 6, based on examination of the subject at the study visits and based on the subject's e-Diary. Only serious adverse events will be investigated during the period from Visit 4 to Visit 5.

*4: Every day until 14 days after each dose, if the subject's symptoms have not returned to normal by Day 14 after receiving the investigational product, then the subject will be asked to, as a rule, fill out the e-Diary until the symptoms return to normal.

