6. HANDLING OF DATA

6.1. Handling of Missing Values

If a value cannot be measured or is the reference value because of, for example, the assessment was not performed, the test value was missing, or there was a problem with the test sample, this parameter will be handled as a missing value.

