7.5. Efficacy Analyses

7.5.1. Primary endpoints

Analysis population(s): FAS

Analysis parameter: The anti-PRP antibody seroprotection (antibody titer ≥ 1 $\mu\text{g/mL}$) rate, and also the seroprotection rates for other antibodies (anti-diphtheria [REDACTED] anti-diphtheria [REDACTED] [REDACTED], anti-PT, anti-FHA, anti-tetanus, anti-poliovirus serotype 1, anti-poliovirus serotype 2, anti-poliovirus serotype 3)

Analysis method: For each analysis parameter, the number of subjects for each time point (4 weeks after the primary immunization, 4 weeks after the booster immunization), the number of subjects assessed for efficacy based on each antibody, the number of seroprotections, the seroprotection rate (%), and the two-sided, 95% confidence intervals will be calculated.

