7.5.2. Secondary endpoints

7.5.2.1 Anti-PRP Antibody Seroprotection (titer ≥ 0.15 $\mu\text{g/mL}$) Rate

Analysis population(s): FAS

Analysis method: Anti-PRP antibody seroprotection (titer ≥ 0.15 $\mu\text{g/mL}$) rate

Analysis method: For each analysis parameter, the number of subjects at each time point (4 weeks after the primary immunization, 4 weeks after the booster immunization), the number of subjects assessed for efficacy, the number of seroprotections, the antibody seroprotection rate (%), and the two-sided, 95% confidence intervals will be calculated.

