7.5.2.2 Antibody Titer Profiles

Analysis population(s): FAS

Analysis parameter: Titers of each type of antibody (anti-PRP, anti-diphtheria [REDACTED], anti-diphtheria [REDACTED], anti-PT, anti-FHA, anti-tetanus, anti-poliovirus serotype 1, anti-poliovirus serotype 2, anti-poliovirus serotype 3)

Analysis method: For each analysis parameter, the number of subjects by time point, the number of subjects assessed for efficacy, the geometric mean, the geometric standard deviation, the two-sided 95% confidence interval of the geometric mean, and the minimum, median, and maximum values will be calculated.

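### The FAS requires a post-primary (Visit 4) titre but is the only population for the booster results, so a child with a valid Visit 6 titre can be left out of every booster estimate

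*SAP*

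**What the plan says.** SAP 5.1 defines the FAS as all enrolled subjects except those never given the product and "Subjects for whom no antibody titer results at all could be obtained at 4 weeks after the primary immunization". Protocol 13.1 has the same rule, and SAP 9 reports no departure from the protocol.

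The FAS is the only efficacy population:

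- SAP 7.5.1 (anti-PRP at 1 µg/mL and the other antigens) names the FAS and asks for "the number of subjects for each time point (4 weeks after the primary immunization, 4 weeks after the booster immunization".
- SAP 7.5.2.1 (anti-PRP at 0.15 µg/mL) names the FAS and asks for "the number of subjects at each time point (4 weeks after the primary immunization, 4 weeks after the booster immunization".
- SAP 7.5.2.2 names the FAS for titres of every antibody: "the number of subjects by time point, the number of subjects assessed for efficacy, the geometric mean, the geometric standard deviation".
- SAP 7.5.3.6 plans no efficacy subset, and Tables 14.2.1, 14.2.2.1 and 14.2.2.2 are all FAS tables.

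Post-booster rates and GMTs are secondary endpoints (SAP 3.1, protocol 5.3.1). Within the FAS, the denominator of a rate is set by SAP 4.2(2): "The number of subjects assessed for efficacy will be the number of subjects for whom antibody titer results have been obtained".

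**The concern.** Membership of the set is decided at Visit 4, but the set is also used for results at Visit 6. A child whose Visit 4 sample was missed or failed has given up nothing that bears on the booster response, yet loses its booster data from the tables. The booster estimates then describe children selected on whether an earlier sample produced a result, rather than all children who were boosted and measured.

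The study makes no tests, so the estimates and their intervals are its whole efficacy output. Each child is 1/30 = 3.3% of the planned sample.

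**Working it through.** **Can such a child exist?** Yes, on three provisions read together.

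1. The window for Visit 5 (dose 4) is "Visit 3 + 6 - 13 months" (SAP 2.3). It runs from dose 3, so missing Visit 4 does not by itself stop dose 4.
2. Protocol 12.1 does not list a missed or failed Visit 4 sample as a reason to discontinue.
3. SAP 6.1 treats a failed sample as missing only: where "there was a problem with the test sample, this parameter will be handled as a missing value".

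**Does another rule bring the child back?** No.

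- The SAP 4.2(2) denominator operates inside the FAS named in SAP 7.5, so it cannot restore someone outside it.
- SAP 5 says "Detailed rules about subject handling will be decided by the study sponsor before the database lock". That allows detail to be added, but no written rule reverses the explicit exclusion.
- Listing 16.2.4 shows titres for all enrolled subjects, but gives no rate, GMT or interval.

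**What does the condition do for the primary rate?** Nothing. A child with no Visit 4 result is outside every Visit 4 denominator under SAP 4.2(2) anyway. Among the efficacy estimates, the condition removes only that child's data at other time points: the Visit 6 rates, and the Visit 1, 5 and 6 titre summaries.

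**Size.** The plan gives no figure for this point. Its one stated probability, 83% in SAP 2.4, reproduces as 1 − 0.942^30 = 0.833 and does not involve the FAS.

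Inputs:

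- n = 30 (SAP 2.4).
- Two-sided 95% intervals (SAP 7.1.1), Clopper-Pearson for rates (SAP 7.1.3).
- Assumptions: all 30 children have a valid Visit 6 titre, and k = 1, 2 or 3 of them have no Visit 4 result. The documents give no k.

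*Rates, when every measured child is seroprotected.* The lower limit for n/n is 0.025^(1/n). *GMTs, with the SD of log titre unchanged.* The half-width is proportional to t(0.975, n−1)/√n, shown relative to n = 30.

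| Children dropped, k | Rate in FAS | Lower 95% limit | Relative width of log-GMT interval |
|---|---|---|---|
| 0 | 30/30 | 88.4% | 1.000 |
| 1 | 29/29 | 88.1% | 1.019 |
| 2 | 28/28 | 87.7% | 1.038 |
| 3 | 27/27 | 87.2% | 1.059 |

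If the dropped children respond like the rest, the cost is therefore 0.3 to 1.2 points on the lower limit and 1.9% to 5.9% on the width of the GMT interval.

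*Illustration only.* Suppose the one dropped child is not seroprotected after the booster and the other 29 are. The table shows 29/29 = 100% (88.1 to 100) instead of 29/30 = 96.7% (82.8 to 99.9), a difference of 3.3 points.

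**The case against.** The strongest reply is that this hardly matters. The study is exploratory and uncontrolled, with no tests and no decision rule for the booster. The primary rates are untouched. The trigger is narrow: a result for any one antigen at Visit 4 keeps the child in, and the excluded child must also receive dose 4 and give a valid Visit 6 sample. The number of such children may be zero. All of that stands, and it limits the weight of the point.

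It can also be said that if missing a Visit 4 result is unrelated to booster response, only precision is lost. That is right. Selection is on having a result, not on its value, and nothing in the documents links a missing Visit 4 sample to a poor booster response. The 29/29 against 29/30 comparison shows what could be hidden, not what is expected.

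A third reply is that the condition has a purpose: it aligns the FAS demographics (SAP 7.3) and the titre profile (SAP 7.5.2.2) with the children who contribute to the primary endpoint. This has some force as a preference. But a child with one antigen result at Visit 4, or no Visit 6 sample, stays in the FAS, so the profile is not a fixed cohort under the present rule either. The reply also does not explain why valid booster results should be left out of the booster estimates.

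Finally, exclusions are visible in the analysis-population table and listing, and the titres are in Listing 16.2.4. A reader could recompute the rates by hand. That softens the consequence but does not replace a planned estimate.

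**Conclusion.** The concern holds. As written, both documents exclude from all booster rates and GMTs any child without a single Visit 4 titre result, even when that child was boosted and has a valid Visit 6 titre. The exclusion brings no gain for the primary rates.

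The structural point rests on the text alone; its size rests on the assumption of 1 to 3 affected children out of 30. On that assumption the loss is small if those children are typical. It is larger, at 3.3 points per child, only if they are booster non-responders and the rest are protected. The primary endpoint is not affected. This should be corrected because correction is cheap, not because it threatens the study's main result.

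**What to change.** Make one of two changes, in the same words in SAP 5.1 and protocol 13.1:

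- define the FAS as enrolled children with at least one dose and at least one post-vaccination antibody result; or
- keep the present FAS for the primary time point and state that the booster rates and GMTs are computed in children who received dose 4 and have a Visit 6 titre. This option also needs the population lines of SAP 7.5.1, 7.5.2.1 and 7.5.2.2 and the titles of Tables 14.2.1, 14.2.2.1 and 14.2.2.2 to match.

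Keep the per-time-point denominator of SAP 4.2(2) in either case. If only the SAP is changed, record the departure from the protocol in SAP 9.

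The cost is wording. The primary and booster cohorts may differ by a child or two, so the titre profile across visits need not be one fixed group; the number assessed at each time point, already planned for the tables, will show this.
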